## 2. STUDY OBJECTIVES AND ENDPOINTS

### 2.1 Study Objectives

#### 2.1.1 Primary Objective

To demonstrate bioequivalence between Permethrin Cream, 5% (Mayne Pharma, Inc.) and Elimate™ in patients with active scabies.

#### 2.1.2 Secondary Objective

To demonstrate comparative safety of Permethrin Cream, 5% (Mayne Pharma, Inc.) vs Elimate™ and tolerability of Permethrin Cream, 5%.

### 2.2 Study Endpoints

#### 2.2.1 Primary Endpoint

The primary endpoint will be the proportion of patients that are identified as cured at Study Day 28. Cure is defined as the absence of new lesions and the healing of all old lesions. Residual, dry, non-inflammatory papules are not counted as active.

#### 2.2.2 Secondary Endpoint

The secondary endpoint will be the proportion of patients that are identified as cured at Study Day 14.

### 2.3 Safety Variables

Analysis of safety variables will be based on all adverse event (AE) capture measuring severity and duration utilizing MedDRA terminology for consistency. Vital signs will also be reviewed and analyzed at the Baseline and at visit 5 (End of Study visit).

### 2.4 Tolerability Assessments

Analysis of tolerability will be based on scores of Stinging/Burning and Itching sensations collected during Patient Self-Assessments at visits 2-5 between the test and reference treatment groups.

## 3. INVESTIGATIONAL PLAN

### 3.1 Study Design

This is a multi-center, double-blind, randomized, two-arm parallel design study to compare the treatment success of the test product, Permethrin Cream, 5% (Mayne Pharma, Inc.), and the Reference product, Elimite™ in patients with active scabies. The diagnosis of scabies is made based on the evaluation of burrows, inflammatory papules and excoriations and with a typical distribution pattern and localization (webbed spaces of the fingers, flexor surfaces of the wrists, elbows, axillae, belt line, feet, skin surface of external genitalia, or areolae), presence of family or contacts with moderate to severe itching which increases during the night, and positive identification of mites, mite eggs, or mite fecal matter (scybala) via microscopic evaluation of skin lesion scrapings [1,2]. Treatment success in this study is based on previously published studies of scabies infestations and defined as the absence of new lesions and the healing of all old lesions due to scabies mites and eggs within the treatment area [5-7]. The assigned investigational product will be applied topically (after washing) preferably in the evening on the day of the Baseline visit (Day 1).

Eligibility criteria requires that all regular bedmates and family members with prolonged physical contact with the subject will agree to be assessed by the Investigator for clinical signs of scabies infestation and receive treatment with standard of care scabicide drug, if necessary. This requirement is detailed in Section 5.8.2.

If signs of active scabies infestation are present at visit 4 (Day 14±2), the study subject will be retreated with a second application of their assigned IP. Household members of the participating study subject will be asked to reapply the standard of care generic Permethrin Cream, 5% at the same visit.

This study is comprised of two phases: screening and treatment. The screening phase will be up to 5 days in duration and treatment phase will be 28±4 days in duration. Approximately 140 subjects (or as many as 228 subjects), at least 12 years of age, male or female, of any race, who meet the inclusion and exclusion criteria, will be enrolled to achieve the desired per protocol subject number. The double-blind randomization of subjects will be in a 1:1 ratio for Test and Reference, and will be stratified by site.

Screening will begin at visit 1 during which informed consent will be obtained from the subject prior to any study-related procedures, and eligibility will be determined by the Investigator. Following receipt of informed consent, the subject's medical history will be recorded along with concomitant medications and, at this point, prohibited treatments must be assessed as they should be discontinued according to the timeframes outlined in section 5.11. A physical examination will be performed for all subjects and a urine pregnancy test will be performed for women of childbearing potential. The subject's scabies infestation will be evaluated for papules and burrows during the visual examination. Presence of acarids, feces, or ova will be assessed via microscopic exam of skin lesion scraping. Subjects who meet all inclusion/exclusion criteria will return to the office for visit 2 within 5 days.

At visit 2 (baseline) the subject's concomitant medications will be updated and any changes to medical history will be recorded. Randomization will occur at this visit and subjects will be instructed on investigational product application and completion of subject diaries. Visits 1 and 2 can be combined, if requirements detailed in Section 6.3.2 are met. All regular bedmates of the subject and individuals with prolonged physical contact with the subject will undergo an assessment by the Investigator and receive one 60 g tube with standard of care generic Permethrin Cream, 5% during the Baseline visit to prevent cross-infestation within the household.

Subject will return at visit 3 (Day 7±1) with the used investigational product tube and subject diaries. Compliance with investigational product applications will be assessed. Safety and tolerability assessments will be conducted.

At visit 4 (Day 14±2), subjects will return for efficacy, safety and tolerability assessments. If signs of active scabies infection are present at this visit, the subject will be treated with a 2nd application of their assigned investigational product as defined in Section 5.6.

Final efficacy, safety and tolerability assessments will occur at visit 5 (Day 28±4). If the subject was retreated, the used tube of the investigational product will be returned at this visit. The duration of each subject's participation in the study will be a maximum of 37 days.

The primary endpoint is the proportion of subjects considered to be cured (defined as the absence of new lesions and the healing of all old lesions) on Study Day 28. To establish bioequivalence, the continuity-corrected, 90% confidence interval for the test-to-reference difference in proportions of subjects cured must be within the equivalence limits -0.20 to 0.20. The evaluation in the PP population will be definitive while that in the mITT population will be considered as supportive.

The secondary endpoint is the proportion of subjects considered to be cured on Study Day 14. Bioequivalence will be assessed using the same approach as in the primary endpoint.

### **3.2 Number of Subjects**

Based on the limited availability of Reference product, a total of approximately 140 subjects, at least 12 years of age, male or female, of any race, who meet the inclusion and exclusion criteria, will be enrolled to achieve a per protocol population of approximately 112 across the United States. Should additional Reference product become available prior to completion of the clinical phase of the study, enrollment will be increased, up to 228, to achieve a per protocol population of up to approximately 182.

---

## 4. SELECTION AND WITHDRAWAL OF STUDY POPULATION

### 4.1 Study Population

Approximately one hundred and forty (140) subjects, and as many as two hundred and twenty-eight subjects, of age 12 years and older with clinical and parasitological confirmation of active scabies will be enrolled in this multi-center study.

### 4.2 Eligibility Criteria

Subjects who satisfy ALL of the following inclusion and have NONE of the following exclusion criteria may be enrolled in the study:

#### 4.2.1 Inclusion Criteria

1. Male or non-pregnant, non-lactating female subject at least 12 years of age or older.
2. Subject must have a positive identification for mites, eggs, or mite fecal matter by microscopic examination of a skin scraping.
3. Subjects must have at least two of the three following: a) excoriations and inflammatory papules with a typical distribution pattern and localization (webbed spaces of the fingers, flexor surfaces of the wrists, elbows, axillae, belt line, feet, skin surface of external genitalia, or areolae); b) presence of burrows; c) family or contacts with moderate to severe itching which increases during the night.
4. Subjects must be willing to make every effort to immediately disinfect clothes, towels, and linens and all potentially infected household items upon diagnosis of infestation to prevent re-infestation.
5. All household members with prolonged physical contact with the subject must be willing to attend Baseline visit and receive treatment with standard of care if deemed necessary by the Investigator in order to prevent re-infestation of the subject enrolled.
6. Subject or representative must read and sign an IRB/IEC-approved Informed Consent Form (ICF); for minor subjects (18 years or younger in most states) the parent or legal guardian should sign the ICF and the child will be required to sign the Assent Form that will be written in such a way as to be understandable to a child.
7. Subject must be able to apply study product to self. If the subject is a child, then parent/guardian will apply study product to him/her.

#### 4.2.2 Exclusion Criteria

1. Females who are pregnant as shown in a urine pregnancy test at the Baseline visit, prior to randomization, or lactating, or of childbearing potential (for purpose of this study a female of

- childbearing potential is considered to be not surgically sterile or postmenopausal for at least 1 year) who are not using or do not agree to use an acceptable form of contraception (oral /implant /injectable /transdermal contraceptives, IUD, condom, diaphragm, or abstinence) during the study, or who intends to become pregnant during the study; contraceptive method must also be consistent throughout the study.
2. Treatment for scabies <4 weeks prior to enrollment, including permethrin, benzyl alcohol, lindane, crotamiton, malathion, and ivermectin.
  3. Use of prohibited medications:
    - Topical or oral scabicial/antiparasitic treatment including: permethrin, benzyl alcohol, benzyl benzoate, lindane, crotamiton, malathion, ivermectin, precipitated sulfur, albendazole, keratolytic cream, tea tree oil, or oil of the leaves of Lippia multiflora Moldenke within 28 days of visit 2.
    - Systemic corticosteroids (including inhaled steroids) taken within 14 days of visit 2.
    - Topical corticosteroids including hydrocortisone taken within 24 hours of visit 2.
    - Topical antipruritics, including antihistamines within 24 hours of any study visits.
    - Oral antihistamine including diphenhydramine (Benadryl) taken within 24 hours of any study visits.
    - Topical antibiotics including mupirocin taken within 24 hours of any study visits.
  4. Patients with immunosuppressive disorders requiring therapy, severe systemic disease, history of HIV infection and/or seizures.
  5. Patients with crusted/Norwegian scabies.
  6. Presence of underlying skin disease that would obscure evaluation of the papules and burrows associated with scabies infection as determined by the Investigator.
  7. Presence of severe cutaneous bacterial or fungal infections requiring therapy (including systemic and topical antibiotics) as determined by the Investigator.
  8. Sensitivity or allergy to Permethrin Cream or any of its components, synthetic pyrethroids, pyrethrin, chrysanthemums or ragweed.
  9. A recent (less than 1 year) history of alcoholism, drug abuse, or other problems which would likely make the subject unreliable for the study.
  10. Participation in another investigational study or using any investigational product within the 30 days prior to the Baseline visit.
  11. Participation of family member, or another member of the household (including regular bedmates) in the current study.
  12. Total number of bedmates and family members with prolonged physical contact is greater than 6 (including study subject).

13. Any employees of the clinic, investigators, or family members of the study staff.
14. Patients who in the opinion of the Investigator would be non-compliant with the requirements of the study protocol.

#### **4.2.3 Criteria for Inclusion of Minor Subjects**

Subjects under the age of 18 must sign the Assent Form that will be written in such a way as to be understandable to a child and to obtain parental or legal guardian consent prior to enrollment in this study. Subjects aged less than 12 years will not be enrolled.

### **4.3 Withdrawal and Early Discontinuation**

In accordance with the Declaration of Helsinki and other applicable regulations, a subject has the right to withdraw from the study at any time and for any reason without prejudice to his or her future medical care. The Investigator, Sponsor, or Medical Monitor may also withdraw the subject at any time if it is medically necessary or in the interest of subject safety.

A subject will be discontinued from this study if any of the following criteria are met:

- Withdrawal of consent by the subject is received
- In the opinion of the Investigator, it is not in the subject's best interests to continue in the study.
- Occurrence of an AE/SAE, which, in the opinion of the Investigator, warrants discontinuation of the subject from the study.
- Pregnancy
- Significant non-compliance with study procedures that would interfere with the study results or increase the subject's risks in the study. This includes known cases of non-compliance of household members with the standard of care treatment.
- If subject is deemed to be a treatment failure, which is defined as any subject whose condition worsens and who requires alternate or supplemental therapy for the treatment of scabies during the study.

Subjects discontinuing, or withdrawing from, the study sooner than their Day 28 visit will undergo the End of Study assessments (as detailed in Section 6.3.5). In addition, if the subject is discontinuing the study and has not returned the dispensed Investigational Product, then the site will remind the subject to return the dispensed investigational product during the End of study visit. In such cases, the Investigational Product dispensed to the subject will be collected and Investigational Product accountability will be performed as per Section 5.10 during the End of Study visit (see Schedule of Activities in Appendix B).

After the End of Study visit, the subject may resume dosing with any medication prescribed by the subject's physician, including Prohibited Medications listed in section 5.11.

If a subject does not return for a scheduled visit, every effort will be made to contact the subject and

document the End of Study visit assessments. The Investigator must document the primary reason for discontinuation of a study subject on the appropriate electronic Case Report Form (CRF).

Randomized subjects who discontinue due to an adverse event will have all events documented and followed to satisfactory resolution, as detailed in Section 7.4.

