
Sponsor:	Name of Finished Product:	Name of Active Ingredient(s):
Mayne Pharma, Inc.	Permethrin Cream	Permethrin, 5%

13. Any employees of the clinic, investigators, or family members of the study staff.
 
14. Patients who in the opinion of the Investigator would be non-compliant with the requirements of the study protocol.
		

Investigational Products, Dose and Mode of Administration:
 
Test Drug: Permethrin Cream, 5%, 60g, topical, manufactured by Mayne Pharma International Pty Ltd.
 
Reference Product: Elimate™ 60g, topical, marketed by Prestium Pharma, Inc. (“Prestium”), the branded subsidiary of Renaissance Pharma.
 
Standard of Care (SOC): Generic Permethrin Cream, 5% 60g available in the market will be used for treatment of the household members with active scabies or at a “high risk” of the disease.
 
Dose During the Active Treatment Period: Subjects will receive a maximum of two doses of the investigational product during the study. The first dose will be applied on Day 1 in an outpatient setting, after the visit to the clinical site (preferably in the evening). The second dose will be applied on Day 14±2 only if retreatment is necessary. Household members will receive one 60 g tube of the standard of care generic Permethrin Cream, 5% at the Baseline visit, sufficient for two applications: at the time of the Baseline visit of the participating study subject, and in two weeks - if the re-treatment will be necessary of the standard of care at Baseline visit.
		

Route: Topical application, covering the entire area of the skin from the neck down to the feet.
		

Study Duration: 28 Days
		

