### **6.3.5 Visit 5: End of Study / Early Termination, and Final Safety Check (Day 28±4)**

The following procedures will be performed:

- Assess adverse events.
- Assess concomitant and prohibited medications.
- Visual examination of skin lesions.
- Vital signs
- Patient Self-Assessment (see Section 6.2.3).
- Pregnancy Test (for females of childbearing potential).
- For subjects receiving second application of the investigational product:
  - Assess subject compliance by reviewing the subject diary. Subject diary will be returned and filed with the subject's source documents (see Section 6.2.4). Both the subject and the study staff will sign off on completed diary.
  - Collect the dispensed investigational product and complete the Site Investigational Product Accountability Log and a Subject Investigational Product Accountability Log.

If the Investigator assesses the subject's condition at any time and determines that the subject's condition has worsened to the degree that it is unsafe for the subject to continue in the study, the subject may be discontinued from the study as treatment failure. Visit 5 Early Termination procedures will be performed, and a standard of care treatment may be advised at the Investigator's discretion.

Subjects discontinuing from the study sooner than the Day 28 visit will undergo the Early Termination (ET) visit at the earliest possible date. If the Investigator decides to discontinue a subject at any time during the study, a standard care of treatment may be advised at the Investigator's discretion, and an EOS/ET visit preferably prior to receiving any standard of care treatment.

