### 8.1 Subject Population/Data Sets to Be Evaluated

The subject populations are defined as follows:

1. **Safety Population:** The safety population is any randomized individual who (a) was enrolled into the study, and (b) received at least one dose of study treatment.
2. **Modified Intent-to-Treat (mITT) Population:** A modified intent-to-treat subject is any randomized individual who (a) met inclusion/exclusion criteria, (b) was enrolled into the study, (c) received at least one dose of the assigned study treatment, and (c) had at least one post-baseline visit.
3. **Per Protocol (PP) Population:** A per-protocol subject is any randomized individual who (a) met inclusion/exclusion criteria, (b) was enrolled into the study, (c) received the assigned study treatment, (d) had not taken any concomitant medications prohibited by the protocol or experienced any major deviations that interfered with or may have interfered with the therapeutic administration of the treatment or the precise evaluation of treatment efficacy, and (e) completed the primary endpoint evaluation within the designated visit window ( $\pm 4$  days).

Subjects whose condition worsens and require alternate or supplemental therapy for the treatment of scabies during the study will be discontinued, included in both the mITT and PP population analyses as treatment failures. Subjects who discontinue early for reasons other than treatment failure will be excluded from the PP population, but included in the mITT population, using Last Observation Carried Forward (LOCF).

Efficacy analyses will be performed using the per-protocol population as definitive and the mITT population as supportive. Safety analyses will be performed using the Safety population.

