14. Listing of Treatment Emergent Adverse Events which lead to discontinuation of study treatment.
15. Listing of Non-Treatment Emergent Adverse Events which lead to discontinuation of study treatment.
16. Listing of Treatment Emergent Adverse Events which lead to Withdrawal from the study.
17. Listing of Non-Treatment Emergent Adverse Events which lead to Withdrawal from the study.
18. Listing of Concomitant Medication.
19. Listing of Serious Adverse Events.
20. Listing of Serious Adverse Events with fatal outcome.
21. Listing of Medical History.
22. Listing of Physical Examination.
23. Listing of Pregnancy test.
24. Listing of Microscopic Examination for Skin Scraping
25. Listing of Subject Vital Signs for Randomized Population.
26. Listing of Inclusion/Exclusion Criteria (Randomized Population).

Figures

1. The proportion of patients that are identified as cured at the Study Day 14 and 28. (mITT population).
2. The proportion of patients that are identified as cured at the Study Day 14 and 28. (PP population).
3. The summary of self-assessment of itching and stinging. (mITT population).
4. The summary of self-assessment of itching and stinging. (PP population).
5. The summary of self-assessment of burning sensations at each visit. (mITT population).
6. The summary of self-assessment of burning sensations at each visit. (PP population).

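### Section 4.3 offers only withdrawal from the study for a qualifying adverse event (or a pregnancy found before Visit 5), so the Day 28 outcome is not collected although the planned single application is already over

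*Protocol*

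**What the plan says.** Protocol 4.3 introduces its list with "A subject will be discontinued from this study if any of the following criteria are met". Two of the entries are "Occurrence of an AE/SAE, which, in the opinion of the Investigator, warrants discontinuation of the subject from the study" and, without qualification, pregnancy.

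The synopsis gives the treatment plan: "The first dose will be applied on Day 1 in an outpatient setting" and "The second dose will be applied on Day 14±2 only if retreatment is necessary". Protocol 5.8.1 agrees that the second application is conditional on the Visit 4 findings.

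On the visit after discontinuation, Protocol 6.3.5 says: "Subjects discontinuing from the study sooner than the Day 28 visit will undergo the Early Termination (ET) visit at the earliest possible date". The Visit 5 procedures, including the lesion examination, are done then.

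On analysis, Protocol 8.1 says: "Subjects who discontinue early for reasons other than treatment failure will be excluded from the PP population". They stay in mITT by last observation carried forward (LOCF), and SAP 4 repeats the rule. PP is definitive and also requires the primary evaluation within ±4 days of Day 28.

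Contact does not end with discontinuation. Under 4.3, subjects who discontinue for an adverse event "will have all events documented and followed to satisfactory resolution", and 6.2.1.6 also continues adverse-event follow-up.

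Protocol 8.3.5 and SAP 5.4.1 plan a summary of events that led to stopping study drug. SAP 8 has a "Listing of Treatment Emergent Adverse Events which lead to discontinuation of study treatment" (Listing 14, with Listing 15 its non-treatment-emergent counterpart), separate from Listings 16 and 17 on withdrawal from the study.

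**The concern.** In a trial with repeated dosing, stopping drug and leaving the study often come close together. Here the planned exposure is complete after the Day 1 application, so ending participation protects the subject from at most one further, conditional application. It also ends collection of the primary outcome.

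Three things follow. First, exclusion from the definitive set depends on an event after randomisation that may be related to formulation, which is what the trial compares. Second, mITT is not a clean check on PP: a lesion examination from, say, Day 7 stands in for an endpoint that needs all old lesions healed by Day 28, and may record non-cure in someone who would have healed later. Third, Reference product is scarce (Protocol 3.2), so each evaluable subject matters.

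There is also an internal mismatch. The safety outputs assume that a subject can stop study drug without leaving the study, but 4.3 does not define that state.

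**Working it through.** **Inputs from the documents.** Decision rule from Protocol 8.3.2 and SAP 5.2.2: the continuity-corrected 90% interval must lie within ±0.20. Reference cure rate 88%; 56 PP subjects per arm for power of at least 0.80, or 91 per arm for at least 0.95 with Test at 86%; 20% allowance for non-PP subjects (Protocol 8.2, SAP 3.1).

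**Assumed, because the documents give no figure:** the share of subjects leaving for adverse events or pregnancy, their arm, and whether they would have been cured.

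**Method.** Every pair of binomial counts is enumerated exactly. Equivalence is concluded when

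L = d − 1.645·se − (1/nT + 1/nR)/2 ≥ −0.20 and U = d + 1.645·se + (1/nT + 1/nR)/2 ≤ 0.20,

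where d is the observed Test minus Reference difference and se is the unpooled standard error in Protocol 8.3.2.

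**Step 1: the plan's own figures.** Power is 0.817 at 56 per arm (88% vs 88%) and 0.952 at 91 per arm (86% vs 88%). Enrolment is 56/0.8 = 70 per arm (140 total), and 91/0.8 = 113.75, rounded up to 114 per arm (228 total). All stated figures reproduce.

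**Step 2: power.** The 20% allowance is 14 of 70 per arm. If some of those 14 were kept in PP:

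| Kept per arm | PP per arm | Power |
|---|---|---|
| 0 | 56 | 0.817 |
| 1 | 57 | 0.824 |
| 2 | 58 | 0.835 |
| 4 | 60 | 0.855 |

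If such losses came on top of the 20% instead, 4 fewer per arm (52) would give 0.773.

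**Step 3: false equivalence.** Take a true Test cure rate of 0.68 against 0.88, which lies on the margin, with 56 PP subjects per arm. If a fraction f of an arm leaves and the leavers have cure rate c, the PP cure rate is (p − f·c)/(1 − f). With f = 0.04:

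| Who leaves | PP Test rate | PP Reference rate | Chance of concluding equivalence |
|---|---|---|---|
| No selection | 0.680 | 0.880 | 0.031 |
| Test only, all cured | (0.68 − 0.04)/0.96 = 0.667 | 0.880 | 0.021 |
| Both arms, all uncured | 0.68/0.96 = 0.708 | 0.88/0.96 = 0.917 | 0.026 |
| Test only, cured at half the arm rate (0.34) | (0.68 − 0.0136)/0.96 = 0.694 | 0.880 | 0.047 |
| Test only, all uncured | 0.68/0.96 = 0.708 | 0.880 | 0.069 |

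For Test-only leavers who are all uncured, f = 0.02 gives 0.047 and f = 0.06 gives 0.101. Leavers whose cure rate equals that of their arm leave the PP rate unchanged, because (p − f·p)/(1 − f) = p.

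**The case against.** The strongest reply is that the rule is narrower than it looks.

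- **Investigator judgement.** The adverse-event entry applies only when the Investigator considers that the event warrants leaving the study. A subject with any lesser event stays in follow-up. A reader might infer that any adverse event ends participation; the text does not say so. This stands and limits the numbers.
- **Pregnancy.** The only scheduled test after baseline is at the End of Study visit (6.2.2.2), when the Day 28 examination is made anyway. Only a pregnancy discovered earlier loses the outcome. This stands.
- **The outcome is not thrown away.** Early Termination includes a lesion examination, and mITT keeps it. This stands: what is lost is the Day 28 observation and PP membership.
- **Routes that reduce bias.** Self-assessed itching and stinging/burning are not recorded as adverse events (6.2.3). Subjects who worsen and need other scabies therapy stay in PP as failures (8.1). Both narrow the group, although other local reactions could still qualify.
- **Retreatment may already be discretionary.** Protocol 5.6.1 and SAP 3.2 say the Investigator may retreat, while Protocol 3.1 and 5.8.1 say the subject will be retreated. These passages need reconciling, but neither version defines a subject who is off product and still in the study.
- **Listings 14 and 15 could simply be empty.** They could, but the planned summary in 8.3.5 and SAP 5.4.1 would still have no defined source.

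A reader might also infer that the rule favours a worse Test product. That needs leavers to come mainly from the Test arm and to be cured less often than the rest of it. The documents support neither assumption, and the calculations move in both directions.

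**Conclusion.** The point holds as a gap in follow-up. For a qualifying adverse event, or a pregnancy found before Visit 5, following 4.3, 6.3.5 and 8.1 as written means that no Day 28 outcome is collected, the subject leaves the definitive analysis, and an early examination stands in for the endpoint in the supportive one. No other section supplies the missing follow-up.

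Its size is unknown and may be small. At the margin with 4% leaving, false equivalence lies between 0.021 and 0.069 against 0.031 without selection; the upper end needs every leaver to be in the Test arm and uncured. Neither a definite inflation of the error rate nor a definite direction of bias can be claimed. The sample size is correct on its own assumptions, and the 20% allowance already covers losses of this kind in general. The power gain shown assumes that 1 to 4 subjects per arm would be recovered and would meet every other PP criterion.

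This is a worthwhile, cheap improvement rather than a flaw that undermines the design.

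**What to change.** In Protocol 4.3 and 6.3.5, separate stopping investigational product from leaving the study. State that subjects who stop product because of an adverse event or pregnancy, and who do not withdraw consent, are still asked to attend the scheduled Day 28±4 lesion examination. Use that result in mITT, and in PP only if every other PP criterion is met, including no prohibited medication. Align Protocol 8.1 and SAP 4, so that the summary in 8.3.5 and SAP 5.4.1 and Listings 14 to 17 have a defined source.

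Keep Early Termination with LOCF for withdrawn consent and loss to follow-up. The treatment-failure rule and decisions on who receives further product are unchanged.

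The cost is wording in both documents and one or two already scheduled, non-invasive visits for a few subjects. Some may decline to return. Others may have used prohibited medication, which 4.3 permits after the End of Study visit, and would remain outside PP.
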